### **Privacy and Data Security**

**In Person:** All hard copy questionnaires will be stored in locked cabinets in the Epidemiology department at CUIMC. Only personnel who have completed human subjects training and are on this protocol have access to these files. No names or other personal- identifying information will be attached to any computerized data.

**Remote Option:** In the event that the consent process (remote e-consent) and questionnaires are administered to participants remotely (sent to participants via email or text message), we will use Columbia's Qualtrics site to obtain e-consent and collect questionnaire data directly from participants. The data generated from the electronically administered questionnaires will be coded and a key will be kept separately on encrypted computers. Only Columbia investigators will have access to the key code. Access to the surveys is available exclusively through an anonymous online link, which is sent directly from Columbia research staff to participants. Access to aggregate data is granted solely to authorized staff via password-protected accounts. All respondent data is saved as a downloadable CSV file in Qualtrics, with information on whether a participant has started, is completing, or has finished the questionnaire, as well as start and end date information. Once data is entered into Qualtrics, data will be downloaded from Qualtrics by Columbia staff and saved on an encrypted endpoint (desktop or laptop computer).

Please note the following process will be adhered to for ANY and ALL aspects of the study in which participant research data is labeled with either their study ID and specimen ID:

**Overall:** The research file that links any information that can identify the participant to the code number will be kept in a locked file cabinet, an encrypted data file, and/or CUIMC IRB approved and encrypted hard or shared drives. Questionnaires and biospecimens will be stored using participants’ unique code number and will not be directly linked to any information that can identify the participant to the code number. Questionnaires, biospecimens, and recorded sessions will be kept in a locked file cabinet, an encrypted data file, and/or CUIMC IRB approved and encrypted shared drives. Only the principal investigator and study staff who have CUIMC IRB

approval for this study will have access to these files. Participant names or any of your information that can identify them will not be used in any reporting of the study results. Transfer of Biospecimen to Collaborators: The urine collection receptacles will have labels with a prepopulated participant specimen ID. [name], study collaborator and director of the 231 Engineering Research Center at Brown University and his team will analyze the biospecimens. We will deidentify the specimen before our collaborators at Brown receive them. Any unused samples will be destroyed by Brown University or mailed back to CUIMC. We are not collecting any genomic data and biospecimens will not be used for whole genome sequencing in this study.

All computers have been updated by the MSPH IT staff to comply with all university standards for encryption. All human subject data that is stored on an End User Devices is always protected by a strong password with the data encrypted at all times. Columbia University will not share or offer the raw data to any third party and we will not publish or disclose confidential data nor infringe on any privacy rights when processing the raw data.

Remote Option: Should the consent (remote e-consent) and questionnaires be administered remotely, information is collected online through Columbia's Qualtrics site. All staff interacting with participants are IRB approved and have completed the required HIPAA and Human Subjects training.

Recording of Group Sessions— We are asking for participants to allow us to record (both audio and video) the key informant and educational intervention sessions. The key informant sessions will not be transcribed.

Specific identifiers that will be recorded: The recordings will include full facial features and participants' first name. We are including this identifiable information in the recording so that we can keep track of what each participant says throughout the discussion. Participants will have the option to turn off their camera on the Zoom app if they prefer not to show their face, in which case they will be identified by their Zoom username that they register with.

People who will have access to the recordings: The transcription company, a registered vendor with Columbia University, will have access to the recording so that they can transcribe what is said during the discussion. We will provide the name of the transcription company and a Service Agreement in upcoming modifications. The key informant sessions will not be provided to the company for transcription.

Clear indication that recording(s) will be kept indefinitely: Identifiers might be removed from the identifiable information and, after such removal, the information or biospecimens could be used for future research studies without additional consent from the participant. Participants are informed in the consent process that their authorization to use and share their research information does not have an expiration (ending) date. They are told that they may revoke consent and authorization at any time and for any reason, and are provided with instructions and contact information for doing so.

Use(s) of the recording(s): The recordings will be used by the research team only for the purposes of analyzing the discussion and not for commercial or educational purposes.

Compensation: Participants will not be provided additional compensation for being recorded; please see the Compensation field of the Subjects section of the protocol for more details on compensation for overall participation.

Mechanisms in place to protect confidentiality of those being recorded: In order to protect participant privacy, the transcription company, FlatWorld Solutions, will only receive a recording of the session that includes the image of their face (should they choose to keep the camera on) and the name the participant provides when they register for the session (their Zoom user name). This is so they can create a “script” of the conversations that take place during the recorded group sessions and keep track of who said what. The transcription company will receive the recording through a secure file transfer system. The image of participants’ face and / or Zoom user name will be attached to their study ID, but, only the CUIMC study team will have access to the file that links the information in the recording to their study ID and that file will be saved on an encrypted computer. Only the transcription company and the study team at Columbia will have access to the recording; study collaborators will only have access to the ‘script’ of the discussion after it has been transcribed by the transcription company. Our contract with the transcription company requires that they destroy the recordings as soon as the script of the session is submitted to and approved by the Columbia research team. After this point, recordings will be stored on an encrypted hard drive that only CUIMC staff has access to.

Clear indication that recording(s) will be kept indefinitely- Identifiers might be removed from the identifiable private information or identifiable biospecimens and, after such removal, the information or biospecimens could be used for future research studies without additional consent from the participant. Participants are informed in the consent process that their authorization to use and share your research information does not have an expiration (ending) date. They are told that they may revoke consent and authorization at any time and for any reason and are provided with instructions and contact information for doing so.

De-identified data will be shared with Rutgers University and WE ACT for Environmental Justice (partners) through an encrypted file sharing service.

Data is collected in private CUIMC offices by phone or mail or in person in the clinical research space provided through CUIMC and the CTSA. Data is only collected by staff members who have completed human subjects training and are approved as part of this protocol. Mechanisms in place to protect confidentiality of those being recorded: In order to protect participant privacy, the transcription company will only receive a recording of the session that includes the image of their face (should they choose to keep the camera on) and the name the participant provides when they register for the session (their Zoom user name). This is so they can create a “script” of the conversations that take place during the recorded group sessions and keep track of who said what. The transcription company will receive the recording through a secure file transfer system. The image of participants’ face and / or Zoom user name will be attached to their study ID, but, only the CUIMC study team will have access to the file that links the information in the

recording to their study ID and that file will be saved on an encrypted computer. Only the transcription company and the study team at Columbia will have access to the recording; study collaborators will only have access to the ‘script’ of the discussion after it has been transcribed by the transcription company. Our contract with the transcription company requires that they destroy the recordings as soon as the script of the session is submitted to and approved by the Columbia research team. After this point, recordings will be stored on an encrypted hard drive that only CUIMC staff has access to.

## **Procedures**

**Objective:** To reduce use of personal care products that contain endocrine disruptor chemicals among women.

The below details the Pilot Intervention

**Study Overview:** To reduce use of phthalate-containing hair care products among women of color. We will apply the Precaution Adoption Process Model (PAPM).

All activities will be performed remote or in person based on IRB mandates. We will submit Questionnaires and Facilitator Forms after initial IRB protocol approval.

## **Specific Aims:**

1. Qualitative Approaches across 5 groups (n=50-100 total participants), we will:

- a. Deliver an educational intervention on harmful chemical exposures, such as phthalates, found in hair care products, developed by the research team using empirical evidence with key informant feedback.
- b. Through focus groups gather participant feedback on content and questions pertaining to intervention and attributes women of color consider when deciding on hair care product use, using a semi-structured guide.

2. Quantitative Approaches using repeat measures, we will:

- a. Using repeated questionnaires to assess PAPM stages, we will assess self-reported behavioral changes in the use of phthalate-free hair care products comparing stage at enrollment to:
  - Stage after the intervention (post-test1),
  - Stage at 1-month post-intervention (post-test2), and
  - Stage at 1-month postpartum (post-test3).
- b. Examine the correlation between self-reported behavioral change assessed by the PAPM questionnaire and
  - Change in self-reported HCP exposure measured via questionnaire (n=50),
  - Change in internal dose of urinary phthalate metabolites (targeted gas chromatography/high resolution mass spectrometry (GC/HRMS) Orbitrap; n=25 with 3-repeat samples),

- (Exploratory) change in internal dose of all-other detectable urinary metabolites (untargeted GC/HRMS-Orbitrap; n=25 with 3-repeat samples).

Questionnaire Constructs : All who wish to enroll and who enroll in the study will be asked to complete the following questionnaires which will be administered preferably via Qualtrix but in paper format if requested.

Eligibility Questionnaire: Confirm that potential participants meet the eligibility requirements (Black or Hispanic women, residing in Northern Manhattan and in the 3rd trimester of pregnancy).

Sociodemographic Questionnaire: Information that includes maternal age, gestational age, race/ethnicity, occupation and educational attainment, and reproductive characteristics and pregnancy details.

Hair Care Product Questionnaire: Asking participants to take stock of current / recent and past hair care product use. This questionnaire was developed by our colleagues at the Rutgers Center for Environmental Exposures and Disease based on / modified from the Women's Circle of Health Study questionnaire that captured a detailed list (including brand name and product) of each hair product each participant used in the last 24-48 hours. This questionnaire is best completed in the space where the woman conducts her everyday hair care routine as she will need to recall product type and name. Therefore, we are sending the questionnaire to be completed at home prior to the educational intervention.

Precaution Adoption Process Model Questionnaire: A 7-stage theoretical model for health behavior change that attempts to explain how an individual comes to decisions to act and how the individual then translates that decision into action. The 'change in PAPM variable' (PAPM) will illustrate how the intervention moves people across staging. Given movement can be fluid, (Rouillon et al. Int J Environ Res Public Health. 2018;15(10), participants will be categorized as progresses (i.e. advancing stage(s) from last reported stage), regresses (i.e. regressing stage(s) from last reported stage), or stagnant (i.e. not moving from last reported step), comparing: pre-test to post-test1, post-test1 to post-test2, and post-test2 to post-test3, and post-test1 to post-test3. Those who progress to Stage 4 will be labeled as negative progresses. We will provide descriptive statistics by pre-test, post-tests, and by the PAPM variable at each time point (when relevant). Using spearman correlations, we will examine independent correlations between PAPM stage at pre-test with each post-test (post-tests1-3). While PAPM staging is not a continuous parameter but ordinal, (Glanz et al. Health Behavior and Health Education: Theory, Research and Practice 4th Edition; 2008) correlations will inform how the intervention moves people across staging.

The PAPM stages for this study are described as follows:

Stage 1: Never heard of endocrine disrupting chemicals (EDCs), nor EDCs in hair care products (HCPs)

Stage 2: Never thought about using phthalate-free HCPs

Stage 3: Undecided about phthalate-free HCPs

Stage 4: Decided not to use phthalate-free HCPs

Stage 5: Decided to use phthalate-free HCPs

Stage 6: Procured and has used (at least once) phthalate-free HCPs

Stage 7: Use phthalate-free HCPs regularly

Research Guides – The Education Intervention Guide and the Focus Group Guide will be developed with the Key Informants and will be submitted for IRB review prior to administration.

Biospecimen Collection, Processing, and Analysis Urine is the preferred biomarker matrix for the hydrophilic phthalate metabolites, whose clearance time is a matter of days and is temporally stable in stored urine samples in spite of their relatively rapid clearance, urine phthalate biomarker measurements are relatively stable over time (days to months); this is likely because exposure sources and patterns of product use are common and fairly consistent. Thus, any changes observed in the urinary metabolites will most likely be due to changes in hair care product practices rather than within-individual variability.

For urine collection, we will follow the CDC urine collection protocol for processing phthalates, and we are asking participants for their first morning urine. Research staff will review the collection procedures with the participants over the phone. Participants will be asked to record date and time of their sample. Urine samples will be stored at or below -20 °C (per the CDC's phthalates urine protocol) within the Biomarkers Core Shared Resource Lab, affiliated with Herbert Irving Comprehensive Cancer Center (Directed by [name]). The urine sample will be assessed for specific gravity to adjust for urine dilution using a refractometer (Adibi JJ, et al. Environ Health Perspect. 2008;116(4):467-473).

Metabolomics: The Biomarkers Core Lab, HICCC (Directed by [name]) will ship to the [name] Lab at Brown University urine samples in cryovials that are packed securely in dry ice. The receiving lab at Brown University will conduct Gas Chromatography / High Resolution Mass Spectrometry-Orbitrap analyses (henceforth GC/HRMS)- Orbitrap analyses) on a random sample of 25 participants, prioritizing participants who have 3 repeat urinary measures and are categorized as progresses or stagnant between PAPM post-test1 to post-test3 (see the study procedure section for this definition). [name] and team (Brown University) will follow an extensive and detailed standardized protocol from [name] for sample preparation and for GC/HRMS for Targeted and Non-targeted Analyses within the HRMS facility located in the new Engineering Research Center at Brown University. In brief, urine samples will be extracted based on EPA Method 8016A for phthalates and phthalate esters (Silva MJ, et al. J Anal Toxicol. 2005;29(8):819-824). Plastics will be strictly avoided to prevent phthalate contamination. The team will assess at minimum 20 LMW phthalates that have been associated with healthier PCP

practices. Sample extracts will be analyzed by [name] and team using a Thermo GC-Orbitrap Q Exactive mass spectrometer analysis performed using Thermo TraceFinder software.

[name] and team will NOT seek to determine genetic predisposition of disease in subjects who are asymptomatic. [name] and team will NOT be conducting any sequencing (whole genome/exome or RNA), nor will they be using any assay/platforms.

**Phase I: Key Informant Session** We will be conducting at least one Key Informant session with our collaborators and partners to design the group educational intervention and focus group session. The Key Informant session will take place via Zoom Webinar or an in-person meeting (dependent on current IRB regulations) and last about 2 hours. Sessions will be recorded. Discussions will include the questionnaire constructs, the content of the educational intervention and script, the message of the intervention and script, and the content of the semi-structured focus group and script. We will also seek feedback from collaborators and partners through Zoom or in-person meetings (dependent on current IRB regulations).

**Phase II: Recruitment, Enrollment, Consent, and Retention** Please see the “Recruitment and Consent” section of the protocol for details. In brief, we will check for participant eligibility, enroll, and consent 50-100 women of color within Northern Manhattan who are early in their 3rd trimester of pregnancy and speak English and/or Spanish.

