### **Specific Aims:**

1. Qualitative Approaches across 5-10 groups (n=50-100 total participants), we will:

- a. Deliver an educational intervention on harmful chemical exposures, such as phthalates, found in hair care products, developed by the research team using empirical evidence with key informant feedback.

b. Through focus groups gather participant feedback on content and questions pertaining to intervention and attributes women of color consider when deciding on Hair Care Product use, using a semi-structured guide.

2. Quantitative Approaches using repeat measures, we will:

- a. Using repeated questionnaires to assess PAPM stages, we will assess self-reported behavioral changes in the use of phthalate-free hair care products comparing stage at enrollment to
  - Stage after the intervention (post-test1),
  - Stage at 1- month post-intervention (post-test2), and
  - Stage at 1-month postpartum (post-test3).
- b. Examine the correlation between self-reported behavioral change assessed by the PAPM questionnaire and
  - Change in self-reported Hair Care Product exposure measured via questionnaire (n=50),
  - Change in internal dose of urinary phthalate metabolites (targeted gas chromatography/high resolution mass spectrometry (known as GC/HRMS) Orbitrap; n=25 with 3-repeat samples),
  - (Exploratory) change in internal dose of all-other detectable urinary metabolites (untargeted GC/HRMS-Orbitrap; n=25 with 3-repeat samples).

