### **The Educational Intervention:**

The intervention will be followed by a question and answer session. The intervention will focus on phthalate reducing behaviors because of the well documented animal and human evidence on their effects on reproductive health and development, they are ubiquitous and added to HCPs to provide scent, detected in human breast milk, urine, amniotic fluid and placenta (suggesting fetal exposure) and phthalate interventions have proven successful. At the end of the intervention, we will also administer a similar Precaution Adoption Process Model Questionnaire to assess the impact of the intervention.

A trained staff member will prior to the start of the educational intervention if taking place in-person:

1. review the consent form with the participant and obtain written consent before the intervention begins
2. Administer the Sociodemographic Questionnaire (participant self-completes or if preferred, completed with interviewer) before the intervention begins.
3. Administer the Precaution Adoption Process Model Questionnaire (participant self-completes) before the intervention begins.
4. Provide the Hair Care Product Questionnaire to be self-completed if they did not complete the questionnaire prior to the session. Or, provide a return envelope if the participant forgot to bring the completed questionnaire with them.

Remote Option: A trained staff member will have gone over the consent process remotely and will send them links from Qualtrix to complete the Sociodemographic Questionnaire and the Precaution Adoption Process Model Questionnaire prior to the educational intervention.

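### A move into or out of PAPM Stages 6-7 between pre-test and post-test1 can be relabelling of unchanged products, yet Aim 2a reads it as behavioral change from enrollment

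*Combined protocol and SAP*

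**What the plan says.** Aim 2a (Specific Aims, under both Study Design and Procedures) states "we will assess self-reported behavioral changes in the use of phthalate-free hair care products comparing stage at enrollment to" three later points: just after the session, one month after it, and one month postpartum.

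The top two of the seven stages are statements about product content: "Stage 6: Procured and has used (at least once) phthalate-free HCPs" and "Stage 7: Use phthalate-free HCPs regularly".

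For in-person sessions, The Educational Intervention has staff "Administer the Precaution Adoption Process Model Questionnaire (participant self-completes) before the intervention begins", and a similar form is given when the session closes. In the remote option the pre-test form is sent by link ahead of the session.

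The PAPM Questionnaire paragraph under Procedures labels each woman "progresses (i.e. advancing stage(s) from last reported stage", "regresses (i.e. regressing stage(s) from last reported stage" or "stagnant (i.e. not moving from last reported step". It applies these labels to four intervals: pre-test to post-test1, post-test1 to post-test2, post-test2 to post-test3, and post-test1 to post-test3. It also plans Spearman correlations of pre-test stage with each post-test stage.

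The Hair Care Product Questionnaire is completed at home, "as she will need to recall product type and name", and is repeated at both follow-ups. Statistical Procedures (Aim 2b Analysis) counts phthalate-containing products and correlates the change with PAPM. Nowhere does a woman's product list set, confirm or qualify her stage.

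**The concern.** A woman is the authority on whether she has heard of something, thought about it or decided on it, which is what Stages 1 to 5 ask. She is not the authority on an ingredient. To place herself correctly at Stage 6 or 7 she must know whether her products are phthalate-free, and the stated hypothesis is that the session raises awareness of phthalates in hair products. The pre-test and the post-tests may therefore measure the top two stages with different knowledge.

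The problem is sharpest at post-test1. When the pre-test is given at the session, there is almost no time to change hair products between the two forms, so a move into or out of Stages 6-7 can hardly be a change in use. The scoring rule still calls it progress or regress, and Aim 2a places it under behavioral change. What is at stake is whether the pilot's change-from-enrollment result describes switching or a mixture of switching and relabelling.

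**Working it through.** **Plan's own figure.** There is none to reproduce. The documents give no power, error rate, effect size or expected stage distribution for the PAPM outcome.

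**Scoring rule applied to illustrative records.** Stages are listed as pre-test, post-test1, post-test2, post-test3. A higher stage than before is progress, a lower one regress, the same one stagnant. The last column is the Aim 2a comparison, which is not one of the four labelled intervals.

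| Record | Stages | Pre to 1 | 1 to 2 | 2 to 3 | 1 to 3 | Enrollment to 3 |
|---|---|---|---|---|---|---|
| A. Mistaken, corrected, truly switches | 7-5-7-7 | regress | progress | stagnant | progress | no change |
| B. Mistaken, corrected, same bottles | 7-3-3-3 | regress | stagnant | stagnant | stagnant | regress |
| C. Learns existing bottles are phthalate-free, same bottles | 2-7-7-7 | progress | stagnant | stagnant | stagnant | progress |
| D. Mistaken throughout, same bottles | 7-7-7-7 | stagnant | stagnant | stagnant | stagnant | no change |
| E. No mistaken belief, truly switches | 2-5-6-7 | progress | progress | progress | progress | progress |

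Against enrollment, the real switcher A cannot be told from D, who changed nothing. B and C appear to move although their use did not. Enrollment to post-test2 gives the same reading as enrollment to post-test3 in all five records. The 1-to-3 column is right for all five. E shows that a woman who starts without a false or missed belief is scored correctly throughout.

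**Size at post-test1.** Every rate here is an assumption; only n = 50 comes from the documents (lower end of the 50-100 planned).
- Regress through corrected belief = n × p × q × c, where p is the share reporting Stage 6-7 at pre-test (0.10 to 0.30), q the share of those who are mistaken (0.30 to 0.70) and c the share corrected by the session (0.80). Low: 50 × 0.10 × 0.30 × 0.80 = 1.2. High: 50 × 0.30 × 0.70 × 0.80 = 8.4. That is 2.4% to 16.8% of women.
- Progress with no product changed = n × u × r, where u is the share unknowingly using phthalate-free products (0.05 to 0.20) and r the share who recognise it in the session. With r = 1, an upper bound: 50 × 0.05 = 2.5 to 50 × 0.20 = 10. With r = 0.80: 2 to 8.

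**Size against enrollment.** Let m be the share of all women wrongly at Stage 7 at pre-test, with half of all women truly switching and every mistaken belief corrected. True switchers showing no change = 50 × 0.5 × m. For m = 10%, 20%, 30%, 40% this is 2.5, 5, 7.5 and 10 of 25 switchers. The same numbers of same-bottle women show regress. For comparison, p × q above spans 3% to 21%, so the two higher values of m are outside it.

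**Effect on a correlation.** An illustrative simulation (2,000 runs, n = 50, half switching, change in use of -2 for switchers plus normal noise with SD 1, mistaken women at Stage 7 and the rest at Stages 1-3 at pre-test) gave a mean Spearman correlation between enrollment-to-post-test3 stage change and true change in use of -0.55 at m = 0, then -0.45, -0.38, -0.33 and -0.30 for m = 10% to 40%. The post-test1-to-post-test3 correlation stayed at -0.52. That stability is built in, because post-test1 stage was drawn independently of the pre-test mistake.

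**The case against.** The strongest reply is that the plan already has an interval that starts after the belief update. The post-test1-to-post-test3 category scores A as progress and B and C as stagnant, all correctly, and it is the interval used to prioritise women for the 25-person urine subsample. This stands. A reader might infer that the scoring rule gives real switchers the wrong sign in general; the documents do not support that. The wrong sign is confined to pre-test to post-test1, and the lost or false change to comparisons anchored at enrollment.

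A reader might also infer that the Aim 2b correlations are corrupted. That is not shown either, because Statistical Procedures does not say which PAPM interval enters them. Product lists and urine are collected before the session and at the two follow-ups, not at post-test1, so a change measured from baseline would match a PAPM interval starting at pre-test. The exposure is possible but depends on an unstated choice.

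The premises are partly inferred. The questionnaires were to be submitted after initial IRB approval and the session guide was still to be developed, so the form may define phthalate-free or prompt a label check, and the session may not reveal the status of a woman's own bottles. Low awareness at baseline could also put most women at Stages 1-3, making false Stage 7 reports rare. All of this limits how often the problem arises; none of it supplies a scoring rule for when it does.

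Finally, the aim is openly about self-report, and Aim 2b compares PAPM with product lists and urine. That is a group-level check, and it does not separate relabelling from switching in the individual stage changes that Aim 2a reports.

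**Conclusion.** The point holds for the enrollment-anchored results: the Aim 2a comparisons, the pre-test-to-post-test1 category and the Spearman correlations of pre-test with post-test stage. In these, a move into or out of Stages 6-7 can be relabelling, most clearly when the pre-test is given at the session. The post-test1-to-post-test3 category is unaffected in the examples worked here.

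The size is unknown. The 1.2 to 8.4 and 2 to 10 women per 50 at post-test1, and the weaker correlations, rest wholly on assumed rates and on the inference that the form takes the woman's word about product content and that the session changes it. Since this is a pilot with no stated decision threshold, and the data for a remedy are already collected, it ranks as a cheap improvement.

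**What to change.** 1. Report pre-test-to-post-test1 moves into or out of Stages 6-7 as their own category, change in product knowledge, and not as behavioral progress or regress.

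2. At enrollment and both follow-ups, derive a verified phthalate-free-use variable from the product classification already planned, with one ingredient rule applied blind to time point. Give unclassifiable products, or products outside the recall window, a separate category. Report Aim 2a change from enrollment on this variable beside the self-reported stage. Treat a Stage 6-7 report with no phthalate-free product listed as unconfirmed, not disproved, since a short recall list cannot refute use on a single past occasion. One listed phthalate-free product likewise does not establish the regular use that Stage 7 requires. Show separately the women at Stages 1-5 who already list only phthalate-free products.

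3. For Aim 2b, state the PAPM interval. Keep the self-reported stage for the correlation with product-list change, because a variable built from that list would be circular there. Use the verified variable only as a sensitivity analysis against urinary metabolites.

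The cost is analysis wording, one derived variable and a little extra analysis on questionnaires already being collected. The downside is that some women will remain unconfirmed or unclassifiable.
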